6.3 Pharmacokinetic Variables

Not applicable.

6.4 Pharmacodynamic Variables

Not applicable.

6.5 Other Variables

The duration of exposure

For each subject and period, the length of time on treatment will be calculated in months, using the following formula.

Treatment duration for 1st line (Months) = (Date of last dose study drug in 1st line-Date of first dose of study drug in 1st line+1)/30.4375

Treatment duration for 2nd line (Months) = (Date of last dose study drug in 2nd line-Date of first dose of study drug in 2nd line+1)/30.4375

Total treatment duration for 1st and 2nd line (Months) = Treatment duration for 1st line + Treatment duration for 2nd line

Total number of study drugs taken

Total number of study drugs taken during the study is calculated as (number of study drugs dispensed at all study visits - number of study drugs indicated as having been returned and lost). Study drugs not returned will be assumed to have been taken.

Treatment compliance

Study drug accountability will be performed to document compliance with the dosing regimen. Subjects will be asked to bring back all remaining study drug at each study visit. Treatment compliance will be defined as the number of study drugs taken during the study divided by the expected number of study drugs, multiplied by 100%.

Treatment compliance for 1st or 2nd line (%)=

[Total number of study drugs taken during 1st or 2nd line]
----- x 100
[Expected number of study drugs during corresponding line]

Expected number of study drugs is calculated as sum for i (Xi x Yi x (assessment date of arbitrary visit i excluding first treatment of each line – date of visit (i-1) +1)) within each line, where i is visit sequence (=2nd ,3rd,...) which include unscheduled visit, X=1 and Y=4 for Enzalutamide plus ADT arm and X=3 and Y=1 for Flutamide plus ADT arm which are number of study drugs to be taken par day according to protocol. When prescribed dose amount is reduced, Y will be changed as reduced number of study drugs.

Example: Expected number of study drugs during corresponding line is calculated as = $(1 \times 4) \times (2016/1/29-2016/1/1+1) + (1 \times 2) \times (2016/2/10-2016/1/29+1)$ for following records are reported;

For patient of enzalutamide plus ADT arm

Date of visit 1st: 2016/1/1 and 4 study drugs per day are prescribed

Date of visit 2nd: 2016/1/29 and 2 study drugs per day are prescribed (e.g. due to AE)

Date of visit 3rd (un schedule): 2016/2/10 and 2 study drugs per day are prescribed (e.g. due to AE)

Previous and concomitant medication

Treatment duration of bicalutamide (Months)=(End date of bicalutamide - Start date of bicalutamide + 1) / 30.4375

Previous and concomitant medication

Previous medication is defined as medication with at least one dose taken 4 weeks (28 days) before Day 1 to the day before initial study treatment.

Sponsor: Astellas Pharma Inc. SAP Version 1.00

ISN/Protocol 9785-MA-3051

Concomitant medication for 1st line is defined as medication with at least one dose taken between the date of first dose (inclusive) of study drug for 1st line AAT and the date of first dose (not inclusive) of study drug for 2st line AAT.

Concomitant medication for 2nd line is defined as medication with at least one dose taken between the date of first dose (inclusive) of study drug for 2nd line AAT and the date of safety visit (inclusive).

Concomitant medication through study medication is defined as medication with at least one dose taken between of first dose (inclusive) and the date of safety visit (inclusive).

PSA doubling time (PSADT)

PSA doubling time is defined from two consecutive PSA measurements (PSA_1, PSA_2) and measured dates (Day_1, Day_2) before study Day 1 as follow;

PSA doubling time (month) =
$$\frac{\ln(2) * 12}{365.25 * \frac{\ln(PSA_2) - \ln(PSA_1)}{Day_2 - Day_1}}$$

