5.1.2 Increase or Reduction in Dose of the Study Drug(s)

If an adverse reaction that falls under Grade 3 or higher according to the National Cancer Institute (NCI)-Common Terminology Criteria for Adverse Events (CTCAE) version 4.0 occurred in association with the study drug during the study period, and is not improved by a proper medical intervention, stop the treatment for a week or until the severity of the adverse reaction improves to Grade 2 or lower. After the improvement, the study drug may be restarted at the original or reduced dose at the discretion of the investigator or subinvestigator.

If a strong CYP2C8 inhibitor (e.g., gemfibrozil) should be used concurrently with the study drug enzalutamide, reduce the dose of enzalutamide to 80 mg once daily. When the CYP2C8 inhibitor is discontinued, return the dose of enzalutamide to the original dose.

The study drug cannot be increased.

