7.3.3 Treatment Compliance

Treatment compliance will be examined for subjects in the ITT population and SAF. For the details of treatment compliance calculation please refer to section 6.5.

Descriptive statistics will be presented for total number of study drugs taken per subject by treatment group and treatment line.

Percent compliance will be summarized in two ways:

- Descriptive statistics will be presented by treatment group and treatment line.
- Percent compliance will be categorized according to the following categories by treatment group and treatment line:
 - o less than 20%
 - o at least 20%, less than 40%
 - o at least 40%, less than 60%
 - o at least 60%, less than 80%
 - o at least 80%, less or equal to 100%
 - o greater than 100%, less than 120%
 - o greater or equal to 120%

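### The SAP's compliance denominator adjusts only Y for a dose reduction, which fails for flutamide if fewer whole tablets per day are prescribed

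*SAP*

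**What the plan says.** SAP section 6.5 defines compliance as units taken divided by units expected, times 100. The numerator covers the whole treatment line: "Total number of study drugs taken during 1st or 2nd line". The denominator is a sum over visits of Xi × Yi × days, where the days are the visit date minus the "date of visit (i-1) +1)) within each line".

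The starting values are "X=1 and Y=4 for Enzalutamide plus ADT arm and X=3 and Y=1 for Flutamide plus ADT arm". For a reduced dose the only instruction is "When prescribed dose amount is reduced, Y will be changed as reduced number of study drugs". X carries a visit index, but no rule says when or how it changes.

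The one worked example is an enzalutamide subject who goes from 4 to 2 capsules a day. The entry that triggers the change begins "Date of visit 2nd: 2016/1/29 and 2 study drugs per day are prescribed (e.g. due to AE", and the example then uses 1 × 2. So Y is set to the number of units prescribed per day. There is no flutamide example.

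Protocol section 5.1.2 foresees reductions for both drugs: after an interruption for toxicity, "the study drug may be restarted at the original or reduced dose". It does not say what a reduced flutamide schedule looks like. SAP section 7.3.3 summarises the result: "Percent compliance will be categorized according to the following categories by treatment group and treatment line".

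**The concern.** The factors do different jobs for the two drugs. For enzalutamide, one intake of four capsules, Y is both units per intake and units per day. For flutamide, three intakes of one tablet (Protocol section 5.1.1), Y is units per intake and already stands at 1. If fewer whole tablets are prescribed per day, the factor that falls is X, and the SAP gives no rule for changing X.

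A programmer following the example would therefore get a wrong denominator for flutamide and a right one for enzalutamide. Under either whole-number reading, flutamide compliance can only be understated. The affected cells are the flutamide lines: first line in the group that starts on flutamide, second line in the group that starts on enzalutamide. A reader comparing the drugs could conclude that flutamide was taken less faithfully than it was, and two programmers could produce different tables from the same text.

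**Working it through.** **Inputs.** X and Y, the Y-only rule, the day count with its +1, and the example dates are from SAP 6.5. Full-dose flutamide of 3 tablets a day is from Protocol 5.1.1. Assumptions: a reduction is to 2 or 1 whole tablets a day; the subject takes every prescribed unit; units taken are counted on elapsed days.

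**Step 1: the SAP's own example.** From 1 to 29 January 2016 is 28 elapsed days, and from 29 January to 10 February is 12. The SAP's expression is (1 × 4) × (28 + 1) + (1 × 2) × (12 + 1) = 116 + 26 = 142 expected capsules. The SAP prints the expression but not the total. Taken: 4 × 28 + 2 × 12 = 136. Compliance: 136/142 = 95.8%. The shortfall from 100% comes from the +1, which counts the visit day shared by two intervals twice. That is a separate matter and affects both drugs.

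**Step 2: expected flutamide tablets per day after a reduction.**

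| Prescribed | Y left at 1 | Y = units per day, as in the example | Y = fraction (2/3 or 1/3) |
|---|---|---|---|
| 2 per day | 3 × 1 = 3 | 3 × 2 = 6 | 3 × 2/3 = 2 |
| 1 per day | 3 × 1 = 3 | 3 × 1 = 3 | 3 × 1/3 = 1 |

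Only the last column is right, and the SAP does not mention a fractional Y. In the middle column, a reduction to 2 a day doubles the full-dose expectation of 3.

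**Step 3: compliance within the reduced interval.** Ignoring the +1:

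- 2 per day, Y=1: 2/3 = 66.7%.
- 2 per day, Y=2: 2/6 = 33.3%.
- 1 per day, Y=1: 1/3 = 33.3%.

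With the +1 over a 28-day interval:

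- 2 per day, Y=1: 56/87 = 64.4%.
- 2 per day, Y=2: 56/174 = 32.2%.
- 1 per day, Y=1: 28/87 = 32.2%.
- Enzalutamide at 2 per day: 56/58 = 96.6%.

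**Step 4: compliance over the line.** Use the example's timing for a flutamide subject, 28 days at full dose then 12 days reduced, with the +1 included:

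- 2 per day, Y=1: taken 3 × 28 + 2 × 12 = 108; expected 3 × 29 + 3 × 13 = 126; 85.7%.
- 2 per day, Y=2: taken 108; expected 3 × 29 + 6 × 13 = 165; 65.5%.
- 1 per day, Y=1 under both whole-number readings: taken 3 × 28 + 1 × 12 = 96; expected 126; 76.2%.

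The first stays in the band of SAP 7.3.3 that starts at 80%. The other two fall into the band from 60% to below 80%. In a longer line, with 5 of 10 four-week intervals reduced, the corresponding scores are 80.5%, 53.6% and 64.4%.

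**Step 5: after the correction.** With prescribed units per day in place of X × Y, and the +1 left in, the same subjects score 108/(3 × 29 + 2 × 13) = 108/113 = 95.6% and 96/(3 × 29 + 1 × 13) = 96/100 = 96.0%. Both are in line with the 95.8% for enzalutamide.

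**The case against.** The strongest reply is that the SAP is incomplete here but not committed to a wrong answer. It describes the factors as daily numbers ("X=3 and Y=1 for Flutamide plus ADT arm which are number of study drugs to be taken par day according to protocol"), indexes both X and Y by visit, and does not require Y to be whole. On that view 6 expected tablets after a reduction is a result no sensible programmer would accept, and Y=2/3 is open to them. The reduced schedule is also unstated: a smaller amount at each of three intakes would fit the Y rule. The SAP refers to table and data specifications outside these documents, which may settle the derivation.

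Part of this stands. A correct reading exists, and the error depends on reductions by whole tablets. But the text names Y alone as the factor that changes, and its only example sets Y to a whole daily count. Nothing in it leads a programmer to a fraction.

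Three stronger conclusions are tempting and are not supported:

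- A reader might infer that every dose-reduced flutamide subject is scored at 33% or 67% while enzalutamide scores 100%. Those flutamide figures belong to the reduced interval, compliance is reported per line, and treatment starts at full dose. Enzalutamide itself scores about 96% because of the +1.
- A reader might want a shift in the flutamide group mean. The documents give no frequency or duration of reductions, and a line spent wholly at the reduced dose is not a course the toxicity rule in Protocol 5.1.2 describes.
- A reader might infer that a poorer flutamide result would be blamed on non-adherence. The plan contains no results, and SAP 7.3.2 tabulates dose reductions and their reasons by group and line, so they can be read beside compliance.

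**Conclusion.** The point holds in a limited form. The Y-only rule gives the right expected count for enzalutamide. For flutamide it gives a wrong one when fewer whole tablets per day are prescribed and Y is kept whole. Flutamide compliance is then understated: to about 67% or 33% within the reduced interval before the +1, and to 85.7%, 65.5% or 76.2% over a line with the example's timing, against 95.8% for enzalutamide. The line figure depends on how much of the line is reduced, which the documents do not let us estimate.

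The consequence is confined to the descriptive tables of SAP 7.3.3. Compliance defines no analysis set and enters no efficacy analysis, and the primary analysis on all randomised subjects is unaffected. The correction is still worth making, because the error runs in one direction and touches one drug in a table that compares the two.

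**What to change.** In SAP section 6.5, replace Xi × Yi by the number of units prescribed per day in that interval, for both drugs: 4 capsules or 3 tablets at full dose, and the prescribed daily count after a reduction. Add a flutamide worked example beside the enzalutamide one. The double-counted visit day could be settled in the same edit, but it is a separate item.

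The cost is one line of text, one example and one program line. The existing example already records units prescribed per day at each visit, so no new data are needed. This concerns the calculation only; no dose or schedule is proposed.

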3.2 Inclusion Criteria

Subject is eligible for the study if all of the following apply:

- 1. Subject must have submitted an informed consent form approved by the institutional review board (IRB) established at each study center prior to the study.
- 2. Age ≥ 20 years at the time of signing the informed consent form.
- 3. Subject is diagnosed with histologically or cytologically confirmed adenocarcinoma of the prostate without neuroendocrine differentiation or small-cell histology.
- 4. Subject on continuous ADT with GnRH agonist/antagonist or bilateral orchiectomy (surgical or chemical castration).
- 5. Subject for whom treatment with effective GnRH agonist/antagonist is to be continued during the study period if bilateral orchiectomy is not performed.
- 6. Serum testosterone level ≤ 1.73 nmol/L (50 ng/dL or 0.5 ng/mL) at screening visit.
- 7. Subject with no change in the dose of bisphosphonate preparation or denosumab for at least 4 weeks if these drugs are used.
- 8. Subject with asymptomatic or mildly symptomatic prostate cancer (BFI-SF score is <4 to Question 3 "the worst pain within 24 hours").
- 9. Subject has an Eastern Cooperative Oncology Group (ECOG) performance status of 0 or 1.
- 10. Subject has an estimated life expectancy of ≥ 12 months.
- 11. Subject is able to swallow the study drug and, comply with procedures required by the study.
- 12. Subject has progression of the disease that falls under at least one of the following 3 criteria during CAB therapy in combination of bicalutamide and ADT.
 - PSA increase should be confirmed at least 2 timepoints with an interval of ≥ 1 week. In at least 6 weeks after the last dose of bicalutamide, PSA should be confirmed higher than the highest PSA measured after the nadir was confirmed during administration of bicalutamide. PSA at screening visit should be ≥ 2 ng/mL (2 µg/L).

- Soft tissue disease progression defined by RECIST guidelines (version 1.1).
- Progression of ≥2 bone lesions defined as new lesions in bone scintigraphy by PCWG2.
- 13. A sexually active male subject and his female partner who is of childbearing potential must use 2 acceptable birth control methods shown below (1 of which must include a condom as a barrier method of contraception) from screening to 3 months after the last dose of the study drug.
 - A male or female condom as a barrier method of contraception;
 - Consistent and correct usage of established, proper use of oral contraceptives;

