4 SAMPLE SIZE

The number of evaluable subjects will be approximately 200 subjects (1st line AAT enzalutamide group: 100, 1st line AAT flutamide group: 100).

The sample size to evaluate the time to PSA progression with 1st line AAT (TTPP1), which is the primary endpoint of the study, was calculated in consideration of the following points:

• Median TTPP1 with enzalutamide: 10.5 months.

- Median TTPP1 with flutamide: 6 months.
 Values reported in the literature: 5 months according to [Okihara et al., 2007], 6.25 months according to [Narimoto et al., 2010].
- The ratio of randomization of 1st line AAT enzalutamide and flutamide groups is 1:1.

- Subject enrollment period is 12 months, and the observation period is 24 months from the enrollment of the last subject.
- Type I error of the two-sided test is 0.05, and power is 90%.
- A log-rank test with the TTPP1 parameters shown above requires 135 events. The
 necessary number of subjects calculated based on the required number of events is 74
 subjects per group.

Required number of events and necessary number of subjects above are calculated with the formulas below based on [Schoenfeld, 1983]. The codes in the formulas are defined as follows.

 M_t : Median TTPP1 in enzalutamide group

 M_c : Median TTPP1 in flutamide group

 t_a : Enrollment period

 t_f : Observation period from the last subject enrollment

 $Z_{1-\alpha}$: 1- α % point of standard normal distribution

 $Z_{1-\beta}$: 1-β% point of standard normal distribution

Hazard in enzalutamide group $(H_t) = \frac{\log_e 2}{M_t}$

Hazard in flutamide group $(H_c) = \frac{\log_e 2}{M_c}$

Hazard ratio for enzalutamide group/flutamide group (HR) = $\frac{H_t}{H_c}$

Required number of events $(N_d) = \frac{4 \times (Z_{1-\alpha} + Z_{1-\beta})^2}{(\log_e HR)^2}$ *The number after the decimal point will be rounded up to the nearest integer.

Incidence of events of enzalutamide group

$$(P_t) = 1 - \frac{1}{6} \left(\exp\left(-H_t \times t_f\right) + 4 \times \exp\left(-H_t \times \left(t_f + \frac{1}{2} \times t_a\right)\right) + \exp\left(-H_t \times \left(t_f + t_a\right)\right) \right)$$

Incidence of events of flutamide group

$$(P_c) = 1 - \frac{1}{6} \left(\exp(-H_c \times t_f) + 4 \times \exp\left(-H_c \times (t_f + \frac{1}{2} \times t_a)\right) + \exp\left(-H_c \times (t_f + t_a)\right) \right)$$

Incidence of events of both groups $(P) = \frac{1}{2} \times (P_t + P_c)$

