7.2.3 Medical History

Summary statistics will be presented for the ITT population and SAF population for numeric variables of:

- Time (months) from initial diagnosis.
- Total Gleason score at initial diagnosis

Frequency tabulations will be presented for categorical variables of:

- Gleason score: primary score + secondary score (< 3 + 3, 3 + 3, 3 + 4, 4 + 3, 4 + 4, 4 + 5, 5 + 4, 5 + 5, other, and missing)
- Total Gleason score category at initial diagnosis (low [2-4], medium [5-7], high [8-10], Unknown or missing)
- Clinical Tumor Stage at initial diagnosis (Tx, T0, T1, T2, T3, T4, Unknown)
- Regional Lymph Nodes at initial diagnosis (Nx, N0, N1, Unknown)
- Distant Metastasis at initial diagnosis (Mx, M0, M1, Unknown)
- PSA progression at study entry (Yes, No)
- PSA doubling time (PSADT)
- Type of disease progression (PSA progression only, radiographic progression with/without PSA progression) at study entry
- Disease localization (bone only, soft tissue only, both bone and soft tissue, and none) at screening
- Target or nontarget soft tissue disease (i.e., at least one target or nontarget lesion per RECIST 1.1) at screening (Yes, No)
- Extent of disease at (bone, lymph node, visceral lung, visceral liver, visceral lung and/or liver, and other soft tissue) screening

In addition, ongoing medical history at randomization which not related to prostate cancer will be summarized by System Organ Class (SOC) and Preferred Term (PT). Medical history ongoing at randomization will be summarized.

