7.8 Subgroups of Interest

Primary efficacy endpoint, TTPP2, PSA Response Rate to 1st Line AAT, PSA Response Rate to 1st Line AAT at Week 13 and rPFS, analyses will be repeated by the subgroups defined on the basis of the categorized variables listed below:

- Baseline ECOG performance status (0 vs \geq 1)
- Age category (<75 and ≥ 75 years), (at or below median vs above median)
- Total Gleason score (≤ 7 and ≥ 8) at diagnosis
- Type of progression (PSA progression only vs radiographic progression with or without PSA progression) at study entry
- Baseline PSA value (at or below median vs above median)
- PSA value at initial diagnosis (at or below median vs above median)
- Baseline LDH value (at or below median vs above median)
- Baseline hemoglobin value (at or below median vs above median)
- Baseline ALP value (at or below median vs above median)
- Treatment duration of bicalutamide (at or below 12 months vs above 12 months), (at or below median vs above median)
- PSA nadir value on CAB therapy ($\leq 4 \text{ng/mL vs} > 4 \text{ng/mL}$), ($\leq 0.2 \text{ng/mL vs} > 0.2 \text{ng/mL}$)
- PSA response rate to 1st line AAT at Week 13 (below 50% vs at or above 50% reduction from baseline), (below 90% vs at or above 90% reduction from baseline) *except for the analysis of PSA Response Rate to 1st Line AAT at Week 13.
- Baseline NLR value (at or below median vs above median)
- Baseline testosterone value (at or below median vs above median)
- Treatment duration of first line hormonal therapy (at or below 12 months vs above 12 months), (at or below median vs above median)
- Disease stages (M0/N0 vs M0/N1 vs M1)
- PSA doubling time (at or below median vs above median)

Also, selected safety variables (treatment emergent adverse events) will be summarized by the treatment group for the subgroups defined on the basis of the categorized variables listed below:

- Baseline ECOG performance status (0 vs \geq 1)
- Age category (<75 and ≥ 75 years), (at or below median vs above median)

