7.11 Handling of Missing Data, Outliers, Visit Windows, and Other Information

Refer to the data specification document in which more details are provided.

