7.11.2 Outliers

All values will be included in the analyses.

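### The SAP's PSA doubling time formula turns negative for a falling PSA, so the median split groups those subjects with the fastest doublers

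*SAP*

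**What the plan says.** SAP 6.5 states that "PSA doubling time is defined from two consecutive PSA measurements (PSA_1, PSA_2) and measured dates (Day_1, Day_2) before study Day 1". The result in months is ln(2) × 12 divided by 365.25 times the daily change in log PSA. The section does not identify which consecutive pair is taken, and it does not say what to do when the second value equals or is below the first.

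SAP 7.8 uses the variable as a subgroup factor: "PSA doubling time (at or below median vs above median". The subgroup analyses cover TTPP1, TTPP2, the PSA response rate to 1st line AAT, the same rate at Week 13, and rPFS. On outliers, SAP 7.11.2 says: "All values will be included in the analyses". For missing data, outliers and windows generally, SAP 7.11 says: "Refer to the data specification document in which more details are provided". That document is not among those available.

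On eligibility, Protocol 3.2 criterion 12 reads: "Subject has progression of the disease that falls under at least one of the following 3 criteria". The three are PSA increase, soft tissue progression and new bone lesions. SAP 7.2.3 anticipates entrants without PSA progression, since it tabulates "PSA progression at study entry (Yes, No" and "Type of disease progression (PSA progression only, radiographic progression with/without PSA progression) at study entry". The same section lists PSA doubling time among the categorical variables but gives no categories.

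**The concern.** A doubling time is meaningful only when PSA rises. A flat or falling PSA is not doubling at all, so it belongs at the slow end of the scale. The formula puts a falling PSA below zero, which is below the shortest genuine doubling time. A split that sends low values to one row then combines the most rapidly rising PSA courses with the falling ones.

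At stake is whether the two doubling-time rows can be read as faster and slower PSA kinetics. Each falling subject in the low row also shifts the median, so a rising subject near the cut crosses into the other row. Both rows become mixtures, and any difference in treatment effect by PSA kinetics is harder to see.

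**Working it through.** The plan states no doubling-time figure to reproduce, so the check applies its formula directly.

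**Inputs**
- Formula: SAP 6.5, PSADT = 12 × ln 2 / (365.25 × [ln(PSA_2) − ln(PSA_1)] / [Day_2 − Day_1]).
- Split: SAP 7.8, at the median, with ties going to the low row.
- N = 200, for illustration, from SAP 4: "The number of evaluable subjects will be approximately 200 subjects". This assumes a usable pair for every subject.
- f, the share of subjects whose chosen pair falls: not in the documents. Assumed 5%, 10% and 15%.

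**Step 1: the formula on single pairs**

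For 8.0 to 7.0 ng/mL over 28 days: ln(7/8) / 28 = −0.004769 per day. Times 365.25 this is −1.742 per year. The numerator is 12 × 0.6931 = 8.318. PSADT = 8.318 / −1.742 = −4.8 months.

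Other pairs 28 days apart (assumed values, ng/mL):

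| Pair | PSADT, months |
|---|---|
| 10 → 20 | +0.92 |
| 10 → 12 | +3.50 |
| 10 → 10.5 | +13.07 |
| 10 → 10.01 | +638 |
| 10 → 10 | undefined |
| 10 → 9.99 | −637 |
| 10 → 9.5 | −12.43 |
| 10 → 8 | −2.86 |

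Every falling pair sorts below the fastest doubling. Two nearly flat courses, 10.01 and 9.99, land at opposite ends of the scale.

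**Step 2: the median split**

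With k = f × 200 fallers and f below 50%, the median is positive, so all k fallers are in the low row of 100. The rest of that row is the 100 − k fastest risers. If fallers were instead ranked slowest, the low row would be the 100 fastest risers. The risers ranked 101 − k to 100, which are those nearest the cut, are therefore in the other row as the SAP stands.

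| f (assumed) | Fallers, all in low row | Share of low row | Risers moved to other row | Subjects whose row changes |
|---|---|---|---|---|
| 5% | 10 | 10/100 = 10% | 10 | 20 |
| 10% | 20 | 20/100 = 20% | 20 | 40 |
| 15% | 30 | 30/100 = 30% | 30 | 60 |

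The count of moved risers depends on the reference. Measured against the risers' own median, which has (200 − k)/2 = 100 − k/2 risers at or below it, the number displaced is (100 − k/2) − (100 − k) = k/2, that is 5, 10 or 15. The count of fallers in the low row is the same either way.

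**Step 3: who can have a falling pair**

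The PSA route in criterion 12 needs a confirmed increase and, at least 6 weeks after bicalutamide, a value above the highest post-nadir value on bicalutamide. Most of these subjects should be rising, although the unspecified pair leaves room for exceptions. The soft tissue and bone routes require no PSA rise, so they are the main source.

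**The case against.** The strongest reply is that the matter may be settled elsewhere. SAP 7.11 defers to a data specification document, and a rule for undefined or negative values could be there. That stands: the supportable statement is that the SAP itself has no rule. It does not remove the point, because SAP 6.5 gives the formula in full and the exception belongs beside it.

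The second reply is that falling pairs may be few. This also stands. The share is unknown, and PSA-route entrants should mostly be rising. The schedule has only one PSA before Day 1, at screening, so the other value of the pair must be historical or unscheduled. Some radiographic-only entrants may have no usable pair and would be missing rather than misplaced.

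The third reply is that the effect is small: this is one of 17 subgroup variables in SAP 7.8, and efficacy by subgroup is an exploratory objective. That is right and limits the weight of the point.

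Two stronger readings are tempting:
- A reader might infer that a real subgroup difference could be reversed. The documents give no share of fallers and no effect by PSA kinetics, so nothing supports this. In a crude two-class model with one effect per class, a row that is 2f from the wrong class shrinks the between-row contrast by 1 − 4f: to 0.8, 0.6 or 0.4 at the assumed shares, which is dilution and not reversal.
- A reader might infer that a baseline mean doubling time is distorted. SAP 7.2.3 plans no such mean; it lists the variable under frequency tabulations.

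**Conclusion.** The point holds as a stated rule that misclassifies. Followed literally, SAP 6.5 with SAP 7.8 and 7.11.2 puts every subject with a falling pair alongside the fastest doublers and leaves equal pairs without a value. The size is conditional: fallers make up 2f of the low row, or 10% to 30% for assumed shares of 5% to 15%, with an equal number of risers nearest the cut moved across under the corrected ranking. This rests on fewer than half of subjects falling, on a computable pair for all 200, and on no contrary rule in the data specification document.

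The consequence is blurred doubling-time subgroup rows for TTPP1, TTPP2, both 1st line PSA response rates and rPFS. The primary TTPP1 test and all analyses in the full ITT population are unaffected. It is worth correcting because the correction is nearly free, not because the trial's main conclusions depend on it.

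**What to change.** - **SAP 6.5:** name the pair used. State that a pair whose second value is equal to or below the first is classed as not doubling and ranked above all positive doubling times. Splitting on the log-PSA slope is an alternative; it is defined for every pair of positive values on different dates and has the right direction.
- **SAP 7.8:** compute the median on that ranking, so that subjects who are not doubling fall in the slower row.
- **SAP 7.2.3:** supply the missing categories by tabulating the number not doubling and the two median-split categories on the same ranking.

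A separate not-rising category would also work if prespecified. If the data specification document already holds a rule, bring it into SAP 6.5. If the SAP is not reopened, its introduction already requires that changes from the planned analyses be justified in the CSR.

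The cost is a few sentences and a small programming change, with no new data.
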